Passive Tactile Stimulation for Stroke Rehabilitation

NCT number: NCT03814889

Unique Protocol ID: 49330

8/26/2022

Protocol

PHASE 1, PHASE 2, and PHASE 3 are pilot studies not included in the clinical trial.

Acute Testing (PHASE 2b): All participants try on several wearable prototypes in our laboratory that provide vibration to the arm. Sensors or electrodes taped onto the arm and hand will sense muscle activity and record any changes during periods of vibration and periods with vibration turned off.

Longitudinal Testing (PHASE 4): This study takes 3 or 6 months. 1) If the patient gets Botox injections in their hand and arm, their arm function will be measured for three months during this standard care. 2) Next, all patients will be given a wearable device to take home. The patient will wear the device while feeling vibrations for 3 hours during the day while awake for two months. During this time and 1 month after this intervention, arm function will be tested.

Statistical Analysis

Wilcoxon Signed-Rank tests were performed for paired comparison on ordinal data (Modified Ashworth) and paired t-tests were performed on paired continuous variables (Active Range of Motion).

Intervention adherence was analyzed by processing device logs using an algorithm.

Acute Stimulation: Our sample size calculations were based on a two-sided paired t-test, which should have adequate power for the Wilcoxon Signed Rank test. For pattern 1 stimulation, we expected the mean change on the Modified Ashworth scale to be -2.3 and the standard deviation to be 0.5. We found that we can achieve 80% power with 4 samples. For pattern 2 stimulation, we expected the change to be -1.1 and the standard deviation to be 0.6. We found that we can achieve 80% power with 6 samples. For pattern 3 stimulation, we expected the change to be -1.0 and the standard deviation to be 0.75. We found that we can achieve 80% power with 9 samples. We enrolled 5 additional participants to account for those who may become lost to follow-up, leading to the sample size of 14 participants.

Longitudinal Stimulation: We expect the average change to be -1.44 in Modified Ashworth scale ratings and the standard deviation to be 1.1 based on prior work [Seim, 2021]. We can achieve 80% power with 16 samples. We aimed to enroll 20 patients to account for drop outs during the study.

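### Do the three separately sized stimulation patterns in the Acute phase need a multiplicity rule?

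*Combined protocol and SAP*

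**What the plan says.** The Acute Stimulation paragraph gives each of three patterns its own expected Modified Ashworth change, standard deviation and sample size for 80% power. For pattern 1, "we expected the mean change on the Modified Ashworth scale to be -2.3 and the standard deviation to be 0.5", which leads to 4 participants. For pattern 2, "For pattern 2 stimulation, we expected the change to be -1.1 and the standard deviation to be 0.6", which leads to 6. Pattern 3, with a change of -1.0 and a standard deviation of 0.75, leads to 9. The total is the largest of the three plus an allowance: "We enrolled 5 additional participants to account for those who may become lost to follow-up, leading to the sample size of 14 participants".

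On method: "Our sample size calculations were based on a two-sided paired t-test, which should have adequate power for the Wilcoxon Signed Rank test". The analysis itself is described once, for both phases: "Wilcoxon Signed-Rank tests were performed for paired comparison on ordinal data (Modified Ashworth".

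The Acute Testing (PHASE 2b) paragraph of the Protocol says: "All participants try on several wearable prototypes in our laboratory that provide vibration to the arm". It does not say that each participant received all three patterns. Neither section states a significance level, a primary pattern, an order of testing, an adjustment for multiple tests, a rule for declaring a pattern effective, or the handling of tied and zero changes.

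**The concern.** Three separate power calculations read like three separate hypotheses, each able to yield its own claim. If benefit is announced for whichever pattern reaches significance, the chance of at least one false announcement exceeds that of a single test, and nothing in the plan limits it. With no stated significance level, a reader cannot work out how often such a statement would be wrong. At stake would be a pattern reported as reducing spasticity on the strength of one of three uncorrected p-values.

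**Working it through.** **Inputs from the plan.** Standardised effects are 2.3/0.5 = 4.6, 1.1/0.6 = 1.83 and 1.0/0.75 = 1.33 for patterns 1 to 3. The test is a two-sided paired t-test at 80% power. The stated sizes are 4, 6 and 9, and the total is 9 + 5 = 14.

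**Reproducing the sample sizes.** Smallest n with at least 80% power, from the noncentral t distribution:

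| Two-sided level (assumed) | Patterns 1 / 2 / 3 |
|---|---|
| 0.05 | 3 / 5 / 7 |
| 0.025 | 4 / 6 / 9 |
| 0.0185 | 4 / 6 / 9 |
| 0.05/3 | 4 / 7 / 9 |

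The stated 4/6/9 is matched exactly at about 0.0185 to 0.025. It also follows from 0.05 if each size is raised by 15% for the rank test (3.45, 5.75 and 8.05, rounded up), but the plan mentions no such allowance. The level therefore cannot be recovered with certainty. The Longitudinal paragraph does not settle it. Its standardised effect is 1.44/1.1 = 1.31, close to pattern 3, yet it states "We can achieve 80% power with 16 samples", which the same method yields only at about 0.001.

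**False benefit when no pattern works, untied scores.** Benefit means significance in the favourable direction only. For independent tests:

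- 0.05 per test: 1 − 0.975³ = 7.3%
- 0.025 per test: 1 − 0.9875³ = 3.7%

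If the same people receive several patterns, the tests are probably positively correlated. The plan gives no correlation, so a range is shown (paired t, 14 completers, simulated):

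| Level per test | Correlation 0 | 0.5 | 0.8 | 0.95 |
|---|---|---|---|---|
| 0.05 | 7.3% | 6.4% | 5.0% | 3.7% |
| 0.025 | 3.7% | 3.3% | 2.7% | 2.0% |
| 0.0185 | 2.7% | 2.5% | 2.0% | 1.5% |

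The benchmark is 2.5%, the false-benefit rate of one two-sided 0.05 test. The exact signed-rank test without ties is similar at 0.05 and 14 completers: 7.2% falling to 3.9% over the same correlations.

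**Ties.** Modified Ashworth is ordinal, so tied and zero changes are to be expected. Normal changes with the plan's standard deviations were rounded to whole or half units, with zeros dropped and mid-ranks used (14 completers). The first figure in each pair is for correlation 0, the second for 0.8.

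- Exact test at 0.05: 1.8% and 1.4% (whole units); 4.1% and 3.2% (half units).
- Exact test at 0.025, independent patterns only: about 0.5% (whole units) and 1.7% (half units).
- Normal approximation without continuity correction at 0.05: 6.8% and 5.5% (whole units); 6.6% and 4.9% (half units). With the correction: 4.4% and 3.5%; 5.5% and 4.2%.

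Across repeated runs with independent patterns, the exact test at 0.05 spans roughly 0.4% to 4%. Giving all three patterns a standard deviation of 0.75 raises its upper end to 4.9%.

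**What Holm would buy and cost.** At 0.05 overall, with untied scores and a paired t-test, Holm brings false benefit to 2.5% or less. The power cost for pattern 3 when it alone works is:

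| Scores, test | 14 completers | 9 completers |
|---|---|---|
| Untied, exact Wilcoxon | 99.4% to 97.3% | 90.2% to 70.7% |
| Tied, half units, exact | 99.1% to 95.8% | – |
| Tied, whole units, exact | 97.7% to 91.1% | about 74% to 53% |

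If all three design effects hold, the cost at 14 completers is under 0.1 point (untied scores).

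**The case for a change.** The strongest case for acting is that the omission is real and costs a sentence to close. Nobody can derive the significance level from the sample sizes, and the two phases cannot share one level under the stated method. The false-claim rate depends on that level and on tie handling, and the plan states neither. If software defaulted to a normal approximation without continuity correction at 0.05, the rate would be about 5% to 7% even with tied scores. Labelling the pattern results exploratory would cost no power.

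The omission stands, and so does the dependence on tie handling. What does not follow is that the analysis is wrong or needs a correction. The plan contains no rule that turns one significant pattern into an efficacy claim. Whether three distinct patterns tried in a laboratory phase form one family needing joint error control is a matter on which statisticians differ. The analysis is also reported in the past tense, so a rule added now could not give prespecified control.

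**Conclusion.** No change to the plan is needed. Part of the point is missing detail: a competent analyst would report the level used and how ties and zeros were treated, and present three small paired comparisons with estimates and confidence intervals. The rest is a fair trade-off. The 7% figure is close to an upper bound and rests on four assumptions: 0.05 per test, independent patterns, a benefit claim for any single significant pattern, and untied scores or an uncorrected normal approximation. At the levels that best fit 4/6/9 the untied rate is 1.5% to 3.7%, on either side of the 2.5% benchmark. With ties and an exact test it is below that benchmark in most settings, though not for half-unit steps at 0.05 with 14 completers. Against that modest gain, a Holm correction would be post hoc. With tied scores and pattern 3 alone working, it would give up about 3 to 7 points of power at 14 completers and about 20 at 9. The conclusion would differ if the report singled out one pattern as proven effective on an uncorrected p-value, which nothing in the documents says it will do.

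### Longitudinal sizing: 16 patients for 80% power does not follow from a mean change of -1.44 and SD 1.1; a two-sided paired t-test needs 7 to 11 pairs

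*Combined protocol and SAP*

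**What the plan says.** The sizing of the longitudinal study is in the Longitudinal Stimulation paragraph of the Statistical Analysis section. Its inputs are: "We expect the average change to be -1.44 in Modified Ashworth scale ratings and the standard deviation to be 1.1 based on prior work". Its result is: "We can achieve 80% power with 16 samples". The enrolment target is then set at 20 to allow for dropouts.

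That paragraph names no test and no sidedness. The Acute Stimulation paragraph just above it does: "Our sample size calculations were based on a two-sided paired t-test, which should have adequate power for the Wilcoxon Signed Rank test". There, three patterns are sized at 4, 6 and 9, each in the same form of words, for example "We found that we can achieve 80% power with 9 samples". For the analysis, the plan says: "Wilcoxon Signed-Rank tests were performed for paired comparison on ordinal data (Modified Ashworth)". Alpha is stated nowhere. The protocol describes no control arm for the longitudinal study: every patient receives the device.

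**The concern.** An expected change of 1.3 standard deviations is very large for a paired comparison, and 16 pairs is far more than such an effect needs for 80% power. Either the power is understated or one of the other items (mean, SD, alpha, test, or what the SD measures) is not the one used to obtain 16.

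This sentence is the only justification for the longitudinal target of 20. If it cannot be reproduced, a reader cannot say how small a change the study could reliably have detected. That matters most if the result is null or the observed change is smaller than expected.

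**Working it through.** **Inputs.** From the Longitudinal Stimulation paragraph: mean change 1.44 in absolute value, SD 1.1, power 80%, n = 16. From the Acute Stimulation paragraph: two-sided paired t-test. Alpha is not stated, so two-sided 0.05, 0.025 and 0.01 are shown. The SD is read as that of the paired change.

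**Formula.** With d = 1.44/1.1 = 1.309, the paired t statistic on n pairs follows a noncentral t distribution with n - 1 degrees of freedom and noncentrality d√n. Power is the probability that it exceeds the two-sided critical value in absolute size.

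**Step 1: try to reproduce 16.** At n = 16 the noncentrality is 1.309 × 4 = 5.24.

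| Two-sided alpha | Smallest n for 80% power | Power one pair below | Power at that n | Power at n = 16 |
|---|---|---|---|---|
| 0.05 | 7 | 72.8% | 82.1% | 99.8% |
| 0.025 | 9 | 78.1% | 85.2% | 99.4% |
| 0.01 | 11 | 78.4% | 84.7% | 98.0% |

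A looser alpha widens the gap (6 pairs at 0.10), and even 0.005 needs only 12. Sixteen is the smallest adequate n only for alpha between 0.00070 and 0.00111; at 0.001, power is 78.7% with 15 pairs and 83.9% with 16.

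**Step 2: use the acute figures as a benchmark.** The same formula shows what alpha the authors may have used and whether their wording marks minimum sizes.

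| Pattern | Mean change / SD | d | Stated n | Alpha range in which it is the minimum |
|---|---|---|---|---|
| 1 | 2.3/0.5 | 4.60 | 4 | 0.0053 to 0.0253 |
| 2 | 1.1/0.6 | 1.83 | 6 | 0.0184 to 0.0372 |
| 3 | 1.0/0.75 | 1.33 | 9 | 0.0159 to 0.0255 |

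All three are minima for alpha between 0.0184 and 0.0253, a range that contains 0.025. At 0.05 they would be 3, 5 and 7. Throughout that joint range the longitudinal inputs need 9 pairs. It does not overlap 0.0007 to 0.0011, so no single alpha gives all four sizes.

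Pattern 3 makes the discrepancy plain: an effect of 1.33 is said to need 9, while an almost equal longitudinal effect of 1.31 is said to need 16.

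**Step 3: the Wilcoxon signed-rank test.** Simulation of the exact test, assuming normally distributed changes without ties, gives minima of 8, 10 and 11 at alpha 0.05, 0.025 and 0.01, with power at 16 of 99.7%, 99.3% and 97.2%. Less favourable versions (rounded changes that create ties, or a relative efficiency of 0.864) raise the need to about 8 or 9 at 0.05 and 13 at 0.01, with power at 16 still about 95% or more. None reaches 16.

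**Step 4: another meaning of the SD.** Suppose 1.1 is the SD of a single rating and visits are uncorrelated, neither of which is stated. The SD of the change is then 1.1 × √2 = 1.556 and d = 1.44/1.556 = 0.926. The minimum n is 12 at alpha 0.05, 14 at 0.025 and 18 at 0.01. Within the acute range of alpha it is 14 or 15. It is exactly 16 only for alpha 0.0133 to 0.0176.

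**Step 5: what 16 completers can detect.** Solving for 80% power at n = 16 gives d = 0.749, 0.843 and 0.963 at alpha 0.05, 0.025 and 0.01. Multiplied by 1.1, these are changes of 0.82, 0.93 and 1.06. Equivalently, at alpha 0.05 a change of 1.44 would give exactly 80% power at 16 only if the SD were 1.44/0.749 = 1.92.

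**The case against.** The strongest reply is that the result depends on two conditions the longitudinal paragraph does not state: that the test is paired, and that 1.1 is the SD of the change. Relax either and 16 can appear. With 1.1 as a single-visit SD, the minimum is 16 at alpha 0.0167 with zero correlation between visits, or at 0.01 with correlation 0.1. An unpaired t-test with 8 per group, 16 in total, has 80.1% power at one-sided 0.05.

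This stands to the extent that the claim must carry its conditions, and one of these routes may be where 16 came from. It does not rescue the sentence. The unpaired route conflicts with the paired analysis and the absence of a control arm. The single-visit route needs an unstated, very low correlation and an alpha stricter than the one that fits the acute sizes, and it departs from the natural reading of an SD quoted beside a mean change.

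It can also be said that 16 patients do give at least 80% power, so the sentence is literally true; that the acute and longitudinal studies could have used different alphas; and that the document is written largely in the past tense, so enrolment will not be reconsidered. The first is correct, but the acute figures show that this wording was used for minimum sizes. The second is possible, but the alpha required would be near 0.001, which nothing in the document suggests. The third limits the consequence to reporting; it does not make the figure right.

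**Conclusion.** The concern holds. If the SD of the paired change is 1.1 and the test is a two-sided paired t-test, the stated 16 compares with 7, 9 or 11 pairs, and the stated 80% with 99.8%, 99.4% or 98.0%, at alpha 0.05, 0.025 and 0.01. Wilcoxon sizing does not close the gap. Because the plan gives no alpha, that range is an assumption.

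The document does not show which item is misreported. On the stated inputs the error is conservative: 16 completers are more than enough, and no power is lost. If instead the true SD of the change was larger than 1.1, that reassurance weakens. With uncorrelated visits and a single-visit SD of 1.1, power at 16 would be 93.3% at alpha 0.05 and 87.3% at 0.025. The sentence should be corrected, but nothing in the conduct of the study turns on it.

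**What to change.** Keep the target of 20. Replace the sentence on power with the values actually used to obtain 16: alpha, sidedness, the test, and whether 1.1 is the SD of the change or of a single rating (with the correlation assumed, if the latter).

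If -1.44 and an SD of change of 1.1 are confirmed, state alpha and replace 80% with the matching power at 16 completers, and add the change detectable with 80% power:

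- alpha 0.05: power 99.8%, detectable change -0.82
- alpha 0.025: power 99.4%, detectable change -0.93
- alpha 0.01: power 98.0%, detectable change -1.06

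These are paired t-test figures, so the text should say so, since the analysis itself uses the Wilcoxon test. The cost is one corrected sentence, with no change to enrolment or procedures.
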